### **3.3 Secondary Study Endpoints**

In addition, location, size, conspicuity, confidence, wall motion deficits and related diagnostic information will be assessed.

## **4 Subject Selection and Withdrawal**

### **4.1 Inclusion Criteria**

All subjects to be entered must:

- be at least 18 years of age and less than 80 years
- if female, be non-pregnant as evidenced by a serum pregnancy test and using a medically-approved method of birth control, or post-menopausal or surgically sterile
- provide written informed consent after having received oral and written information about the study
- patients with ischemic or dilated cardiomyopathy with an EF less than or equal to 50 or patients with paroxysmal or persistent atrial fibrillation
- Have completed the MRI checklist and do not have exclusions to having an MRI
- 

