## 1.1 Background

- This is a first-in-human clinical translation of manganese-enhanced MRI(MEMRI) to assess the peri-infarct injury in patients with patients with ischemic or dilated cardiomyopathy with an EF less than or equal to 50 or patients with paroxysmal or persistent atrial fibrillation
- and those who received stem cell therapy for these indications. The PI recently obtained an approval for an Investigational New Drug (IND # [REDACTED]) to conduct a clinical trial of MEMRI contrast agent (EVP1001-1, Eagle Vision, Downingtown, PA). Funding of this proposal will enable a clinical trial of 120 patients with ischemic or dilated cardiomyopathy with an EF less than or equal to 50 or patients with paroxysmal or persistent atrial fibrillation to evaluate the safety and efficacy of sequential acquisition of MEMRI and delayed-enhanced MRI (DEMRI) for precise tissue characterization of the peri-infarct region (PIR). This novel technique designed to integrate the biology of the viable cardiomyocytes with the anatomy of the scar will predict future cardiovascular events (CVE), in this highly morbid patient population. ICM and NICM are the primary etiology of advanced heart failure (HF) while ACM is a frequent sequela of HF. Today, HF is the leading diagnosis of hospital admission in the US. Our studies have confirmed a direct association between the presence of PIR and the occurrence of atrial and ventricular arrhythmia and remodeling, resulting in high morbidity and mortality in advanced HF. PIR has been recognized as an important substrate to trigger atrial and ventricular arrhythmias and stem cells may provide an alternative therapy for PIR. Studies employing DEMRI has identified atrial scar as the potential cause of atrial arrhythmia. This proposal contains novel hypotheses well-grounded on the following 2 innovations: (1) MEMRI for management of HF. An alternative approach is to employ manganese (Mn2+), which targets the viable myocardium. Mn2+ is specific to the L-type calcium channels and complements the non-viable scar delineated by DEMRI. The dual MEMRI-DEMRI approach will, therefore, identify the viable and, potentially, salvageable cardiomyocytes outside the core infarct zone but inside the PIR. Our recently published study demonstrated that an overlap of DEMRI and MEMRI signal denoted a significant number of live cardiomyocytes (MEMRI-positive) within the non-viable (DEMRI-positive) region. This innovation will profoundly impact the clinical management of the advanced HF patients and AA patients including atrial fibrillation. EVP1001-1 allows highly effective intracellular targeting of viable cardiomyocytes with high level of safety and unique magnetic properties. (2) Assessment of therapeutic response using MEMRI. EVP1001-1 is rapidly transported, intra-cellularly, to mitochondria rich tissue such as heart, liver, and kidney, demonstrating significant enhancement indicative of cell metabolism and viability. High dose clinical safety studies of SeeMoreTM with safety index of 45-90 correspond more favorably than the widely used clinical imaging agents (10-20 for iodinated X-ray products and 20-60 for gadolinium). This specific, non-perfusion dependent distribution due to active intracellular uptake is one of the key attributes that offers real-time assessment of therapeutic response, using cardiac cellular imaging. A clinical safety trial in 6 patients have demonstrated negligible uptake in the intra-infarct region (IIR), reduced uptake in the PIR, and significantly higher uptake in the normal tissue to generate positive signal. In this trial, the mean LVEF was 32±4%. The DEMRI vs. MEMRI (scar/myocardial volume) demonstrated significantly higher measurement of the scar by DEMRI in all patients (39±11%\* vs. 16±3%, \*p<0.01) These data indicate 2 important findings: 1) significant over-estimation of the scar by DEMRI and 2) quantitative difference of the scar volume between MEMRI and DEMRI delineates the PIR. This precise characterization allows accurate assessment of the efficacy of novel therapeutic agents in restoring the PIR at both cellular and tissue levels. EVP1001-1 is a new manganese (Mn)-based intravenous imaging agent being developed to enhance magnetic resonance imaging (MRI). While Mn has long been known to have desirable magnetic and kinetic properties for MRI, use in humans was not initially possible due to cardiovascular depression and electrocardiogram (ECG) changes, including prolongation of PR and QTc intervals, associated with intravenous administration. Chelation of Mn, as had been done with gadolinium for use with MRI, provided relevant safety, but sacrificed desirable magnetic and kinetic properties. EVP1001-1 provides Mn in a form that maintains the desired magnetic and kinetic properties while overcoming the cardiovascular toxicity of Mn. EVP1001 is taken up into heart cells (primarily via addition of calcium to avoid cardiotoxic effects; please refer to patent listed below). The potential to distinguish healthy heart tissue from unhealthy heart tissue based on a specific sustained pattern of enhancement provides a basis for evaluating the performance of EVP1001-1 in heart patients. MRI offers benefits over other imaging technologies. Relative to radioactive nuclear imaging procedures, MRI is 3- dimensional, provides good soft tissue discrimination, and is of high spatial and temporal resolution. These features have been reported to identify smaller defects (e.g., subendocardial infarcts) and match angiographic results more closely than other modalities such as SPECT. It may be possible to enhance the utility of MRI for heart disease further through the use of an imaging agent that is specifically taken up into heart cells. EVP1001-1 is the only cardiac-specific agent being developed for this purpose. Unlike nuclear perfusion agents, EVP1001-1 is not radioactive and does not require special handling, shielding, transport or storage. In addition, the specific pattern of enhancement achieved in the heart muscle persists

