#### *Primary Objective*

Specific Aim 1 evaluates the efficacy of MEMRI-DEMRI to characterize the peri-infarct injury in the ventricles and atria.

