### **4.2 Exclusion Criteria**

- have a positive pregnancy test (females)
- received an investigational drug or device within 30 days prior to administration of EVP1001-1

- have known hypersensitivity to ondansetron or other selective serotonin 5HT3 receptor blockers
- are taking a digitalis preparation or calcium channel blocker within 30 days to MRI
- Contraindication to receiving metoprolol
- have a history of torsades or prolonged QT/QTc interval (QTc > 470 msec)
- have NYHA Grade IV heart failure or EF less than 25
- have abnormal liver function tests or a history of liver disease (2 times upper limits of normal)
- have stage 11 hypertension (Systolic Blood Pressure > 140 or Diastolic BP > 90 consistently at baseline)
- have abnormal baseline potassium or calcium (outside normal reference ranges)
- hemoglobin less than 10 g/dl
- Have a history of ventricular arrhythmia per stress test or monitoring
- No recent cardiac intervention within 90 days (CABG, Valve, PTCA)
- No recent CHF, MI or Angina within 60 days
- Conduction disease (QRSd >120 msec or Sick Sinus Syndrome.)
- No cardiac implantable device
- Weight not to exceed 300 kgs and/or chest circumference .36cms
- 

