## 7 Statistical Plan

### 7.1 Sample Size Determination

The total number of 0 patients will power this study adequately, however as we have extended the protocol to include the atrial fibrillation participants (and extra 60 pts) the difficulty in imaging the atria, coupled with the thin atrial walls, means that we expect a difference in DEMRI volume of 40 (+ or - 20) in participants with early disease and 60 (+ or - 20) in participants with advanced disease. Accordingly, 60 participants will be needed for the additional cohort. Our published pre-clinical study in 13 swine demonstrated the infarct volume percentage difference of 9% between MEMRI and DEMRI ( $p<0.001$ ). This difference will enable significant delineation of the changes in the peri-infarct viability between the cell therapy and control arms. The preliminary porcine data presented above demonstrated a mean of 100% increase in the CNR of the peri-infarct region and a mean of 50% decrease in the scar volume, suggesting robust MEMRI signal detection of stem cell engraftment and increased peri-infarct viability. Furthermore, the clinical trial in 6 ICM patients demonstrated significant difference in the infarct volume between MEMRI defect and DEMRI enhancement. This difference between MEMRI and DEMRI represents PIR assuring reliable detection of the PIR. Employing these data, in order to detect a mean difference of 20% in MEMRI signal of stem cell engraftment and MEMRI-DEMRI signal of peri-infarct viability with a standard deviation of 5%, the t-test sample size calculation in this study has 90% power at the alpha 0.05 significance level, assuming an equal variance between the two distributions.

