### 7.3 Subject Population(s) for Analysis

We expect to enroll 60 patients with various cardiomyopathies including NICM, ICM, and ACM (dilated cardiomyopathy, ischemic cardiomyopathy, and atrial cardiomyopathy). Our goal is to demonstrate improved sensitivity and specificity of identifying viable myocardium and PIR in the ventricles and atria in various cardiac patients to help improve clinical management

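### Peri-infarct region is sought in ischemic, non-ischemic and AF patients alike, with no infarct required and no split analysis, so the MEMRI-DEMRI difference mixes two quantities under one name

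*Combined protocol and SAP*

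**What the plan says.** **Who enters.** Section 4.1 takes "patients with ischemic or dilated cardiomyopathy with an EF less than or equal to 50 or patients with paroxysmal or persistent atrial fibrillation". The only rule on infarction, in section 4.2, is negative: "No recent CHF, MI or Angina within 60 days". An older infarct is allowed but not required.

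**What is sought.** The primary objective in section 2 reads: "Specific Aim 1 evaluates the efficacy of MEMRI-DEMRI to characterize the peri-infarct injury in the ventricles and atria". The Study Summary states the objective as assessing peri-infarct injury in ICM, NICM and AF. Section 7.3 describes the analysis population in one sentence, "We expect to enroll 60 patients with various cardiomyopathies including NICM, ICM, and ACM", and sets the goal of "identifying viable myocardium and PIR in the ventricles and atria in various cardiac patients".

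**How the measure is read.** Section 1.1 concludes from the pilot that the "quantitative difference of the scar volume between MEMRI and DEMRI delineates the PIR". Section 7.1 says: "This difference between MEMRI and DEMRI represents PIR assuring reliable detection of the PIR".

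**On what evidence.** Section 7.1 relies on a published swine study and on the pilot: "the clinical trial in 6 ICM patients demonstrated significant difference in the infarct volume between MEMRI defect and DEMRI enhancement". The validation in section 1.3 is in swine infarcted by balloon occlusion of the LAD.

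**How it is analysed.** Section 7.2 gives a Student's t-test of MEMRI against DEMRI and a Pearson correlation of engraftment or peri-infarct viability with function or outcome. Neither is split by etiology or by infarct status.

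**A second definition of efficacy.** Sections 3.1 (Parameters to be Measured) and 3.2 base efficacy on whether infarct or ischemia is present. Section 3.1 derives sensitivity, specificity and predictive values; section 3.2 uses echo and gadolinium MRI as the standard, together with patient outcomes.

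**The concern.** A region can be peri-infarct only if there is an infarct. In a subject without one, a MEMRI-DEMRI difference must come from something else: diffuse fibrosis, for example, or measurement error in a thin wall (7.1 itself warns about imaging the atria). The plan gives that difference no other name and no separate analysis.

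The stake is the meaning of the result under Aim 1. A pooled difference can be clearly significant and still not be the size of the PIR in anyone. The correlation with outcome is exposed in the same way. If the three cohorts differ both in mismatch and in event risk, pooling can create or hide an association that has nothing to do with peri-infarct viability.

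**Working it through.** **1. The plan's own figures.** Section 7.1 claims 90% power at alpha 0.05 for a mean difference of 20% with SD 5%. Taking these as the mean and SD of within-subject differences (an assumption, since 7.1 does not say), a two-sided paired t-test already reaches 90.8% with 3 subjects. At 50, 60 or 120 subjects, the totals that appear in different sections, power is about 100%. The stated 90% therefore matches none of those totals. The AF cohort is sized on something else: DEMRI volume of 40±20 in early against 60±20 in advanced disease. Sixty patients (30 per group) give about 97% power for that contrast. It compares stages within one modality, and no MEMRI-DEMRI difference is assumed for the atria.

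**2. What the evidence covers.**

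| Cohort | Infarct required at entry | MEMRI-DEMRI data given | PIR or peri-infarct injury sought |
|---|---|---|---|
| ICM | No (likely in many) | 6 patients: scar 39±11% by DEMRI, 16±3% by MEMRI | Yes |
| NICM | No | None | Yes |
| AF | No | None | Yes |

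The swine data (9% difference, 13 animals) also come from infarct.

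**3. What a pooled mean estimates.** Let f be the share with an infarct, d their mean difference and m the mean difference in the rest. Then

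pooled mean = f·d + (1 − f)·m.

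The pilot gives d = 39 − 16 = 23 points. The documents give neither f nor m. Suppose f = 1/2:

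- m = 0: 0.5 × 23 + 0.5 × 0 = 11.5
- m = 23: 0.5 × 23 + 0.5 × 23 = 23

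A pooled mean of 11.5 would also arise with f = 0 and m = 11.5, that is, with no infarct in the sample. The pooled figure alone cannot say how much of it is PIR. This holds for any f below 1.

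**4. Dilution, if m = 0 is assumed.** With d = 23, the pooled mean is 11.5 at f = 1/2, 23/3 = 7.7 at f = 1/3, and 23/4 = 5.8 at f = 1/4.

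**5. Does this cost power?** With m = 0 and within-group SD s, pooled SD = √(s² + f(1 − f)d²). For d = 20, s = 5, f = 1/4: √(25 + 0.1875 × 400) = √100 = 10, with mean 5. Two-sided paired power at N = 50 by this formula:

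| d, s | f = 1/2 | f = 1/3 | f = 1/4 | f = 0.10 |
|---|---|---|---|---|
| 20, 5 (section 7.1) | >99% | 99% | 93% | 43% |
| 9, 5 (swine difference) | >99% | 89% | 69% | 19% |
| 20, 20 (SD borrowed from the AF figures) | 87% | 55% | 36% | 10% |

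Simulation with a fixed number of infarct subjects gave 99.6% for the first row at f = 1/4 and 38% at f = 0.10. On the plan's own inputs, power is kept unless infarcts are rare. Serious loss needs a smaller difference, a larger SD or a low infarct share, and the documents establish none of these for this trial.

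**The case against.** The strongest reply is that infarct-free subjects are useful. Under the efficacy definition in 3.1 and 3.2 they are the negatives, and a sample made up only of infarct patients could not yield patient-level specificity. This stands, and it rules out a remedy that removes them. It does not settle the reading of the difference in 7.1 to 7.3: calling mismatch PIR in those negatives would count against the very specificity they are there to measure.

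Second, the statement in 7.1 that the difference represents PIR follows directly on the 6 ICM patients, and the one in 1.1 interprets the same pilot. Neither is written as an analysis rule for NICM or AF. That is fair. The extension to all cohorts comes from the Study Summary, Aim 1 and 7.3, and no section limits it again.

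Third, 7.1 calls the AF patients an additional cohort with its own rationale and number, and 1.1 names atrial scar as a possible cause of atrial arrhythmia. So AF is partly set apart, and no text says AF patients enter one ventricular mean. But 7.2 and 7.3 do not carry the separation into the analysis.

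A reader might also infer that dilated cardiomyopathy and AF patients cannot have the target lesion. The documents do not support that. Section 4.2 excludes only infarction within 60 days, so some of them may have an older infarct.

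**Conclusion.** The point holds as a fault in what is estimated. The plan requires no infarct, seeks PIR in three cohorts, has evidence for the PIR reading in infarct only, and specifies one unsplit comparison and one unsplit correlation. As written, mismatch of other origin could be pooled with PIR or reported as PIR.

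The size cannot be fixed from the documents. The fall from 23 to 11.5 points needs two assumptions, half the subjects with an infarct and zero difference in the rest, and the 23 points rest on 6 patients. A reader might conclude that the trial is underpowered for this reason. That is not shown: at the plan's 20% and SD 5%, power at 50 subjects is still 93% with one quarter infarcted. Nor does it follow that the whole efficacy analysis fails, since the presence-or-absence endpoint in 3.1 and 3.2 is a separate one that can use every subject.

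This should be fixed, and before results are seen, because an infarct subset chosen afterwards would be post hoc.

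**What to change.** Change sections 7.2 and 7.3, and leave eligibility as it is:

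- Run the MEMRI-DEMRI comparison and the correlation with outcome separately for the ICM, NICM and AF cohorts.
- Restrict the term PIR, and any PIR estimate, to subjects of any cohort with a documented prior infarct. Take infarct status from the cardiac history already collected under 3.1. Do not take it from DEMRI, which is one of the two methods compared.
- In all other subjects, call the difference MEMRI-DEMRI mismatch, and report the atrial part of Aim 1 under that name. Confining Aim 1 to ICM would drop its atrial part and any dilated cardiomyopathy or AF patient with an old infarct.
- Keep all subjects in the sensitivity and specificity analysis of 3.1 and 3.2, with infarct-free subjects as negatives.
- State the expected number in each cohort and the expected number with a prior infarct, so that the precision of the PIR estimate can be judged.

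The cost is protocol wording and some extra analysis, with no added patients or procedures. The price is a smaller set for the PIR estimate and a narrower PIR claim.

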### **4.2 Exclusion Criteria**

- have a positive pregnancy test (females)
- received an investigational drug or device within 30 days prior to administration of EVP1001-1

- have known hypersensitivity to ondansetron or other selective serotonin 5HT3 receptor blockers
- are taking a digitalis preparation or calcium channel blocker within 30 days to MRI
- Contraindication to receiving metoprolol
- have a history of torsades or prolonged QT/QTc interval (QTc > 470 msec)
- have NYHA Grade IV heart failure or EF less than 25
- have abnormal liver function tests or a history of liver disease (2 times upper limits of normal)
- have stage 11 hypertension (Systolic Blood Pressure > 140 or Diastolic BP > 90 consistently at baseline)
- have abnormal baseline potassium or calcium (outside normal reference ranges)
- hemoglobin less than 10 g/dl
- Have a history of ventricular arrhythmia per stress test or monitoring
- No recent cardiac intervention within 90 days (CABG, Valve, PTCA)
- No recent CHF, MI or Angina within 60 days
- Conduction disease (QRSd >120 msec or Sick Sinus Syndrome.)
- No cardiac implantable device
- Weight not to exceed 300 kgs and/or chest circumference .36cms
- 

#### **4.3 Subject Recruitment and Screening**

This is an open-label, baseline-controlled study to be conducted. Adult male or non-pregnant female patients who have been referred for evaluation of cardiomyopathy and atrial fibrillation and patients who have received stem cell therapy related to these indications will be recruited. An initial cohort study of 6 patients to conduct safety evaluation was conducted before proceeding with 120 additional patients. In the initial cohort, a patient was dosed based on the Phase 1 and 2 clinical trial data evaluation completed by Eagle Vision Pharmaceutical, Inc. Subjects were excluded if they had received an investigational device within 30 days prior to administration of EVP1001-1; had a history of drug abuse or alcoholism; were taking a digitalis preparation; had a history of torsades; had NYHA Grade IV heart failure; had abnormal liver function tests or a history of liver disease; had uncontrolled hypertension; had abnormal calcium, potassium or hemoglobin values at baseline; if they develop a cardiac arrhythmia prior to or during either of the exercise tests-- EVP1001-1 was not administered. The same parameters will apply to the new group of subjects.

### **5 Study Drug**

#### **5.1 Description**

The active ingredient is EVP 103 and is provided as a sterile, non-pyrogenic powder in 50 ml vials. Please see 5.4 for preparation instructions

#### **5.2 Treatment Regimen**

The proper dose should be specified in the protocol on a "per kilogram body weight" (0.28 ml/kg) basis and must be given slowly over approximated one (1) minute intravenously. This same administration rate applies to flushing residual drug in connecting tubing/injection port.

#### **5.3 Method for Assigning Subjects to Treatment Groups**

Not Applicable

#### **5.4 Preparation and Administration of Study Drug**

The active ingredient is EVP 103 and is provided as a sterile, non-pyrogenic powder in 50 ml vials. Prior to administration, Drug will be prepared as follows: Using aseptic technique, transfer via syringe 10 ml of 10% Calcium Gluconate, USP and 30 ml of Sterile Water for Injection to a vial containing EVP 103. Shake gently to dissolve the powder. This prepares 40 ml of Drug. Drug should be used promptly (within 1 to 2 hours) following preparation. The calculated osmolality of Drug is 0.27 (nearly isomolar) and the pH is slightly acidic to neutral (5.5 to 7.0).

CONFIDENTIAL

This material is the property of Stanford University. Do not disclose or use except as authorized in writing by the study sponsor

Dilutents and drug product should be inspected to assure that a clear solution is present. Should any precipitate or undissolved material remain in the vial, the vial should be gently warmed and shaken gently to dissolve any visible material prior to either dilution or administration

## **5.5 Packaging**

Drug will be supplied as a non-pyrogenic powder in 50 ml vials.

- Shipped in boxes of 30 vials each
- Labeling:

*EVP 103: Sterile Lot No: 11211114  
CAUTION: FOR INVESTIGATIONAL USE ONLY  
Contents: 1161umol of EVP 103  
Store at room temperature  
Stanford University Medical Center  
[name]  
Expiration: 0612019 Vial #'s: 0001 - 0030*

